7.1 Baseline assessment, randomization and treatment

After having obtained informed consent from the subject, the baseline assessment begins at the treatment visit (TV) prior to randomization and IMP administration. It ends once all pre-randomization assessments have been completed. No trial specific procedure must be performed before the subject and the Investigator, or designee, have signed and dated the ICF. Signing the ICF defines the start of the trial. The time of signing the ICF and of the baseline assessments should be recorded in the source documents and on the CRF. Please refer to section 6.3 for details on timing of baseline assessments.

The required procedures may be done on different calendar days, however the day of randomization and treatment (IMP administration) is considered Day 0 (D0).

After ICF signature and prior to randomization, the following baseline assessments will be performed:

- Inclusion and exclusion criteria qualification (see 6.5.1.);
- Demography/baseline characteristics;
- Medical history;
- Hearing loss onset;
- Prior and concomitant medication;
- Tinnitus evaluation (history and characteristics);
- General physical examination, body weight, height;
- Vital signs (blood pressure, temperature, pulse);
- Tinnitus presence or absence and numerical rating scales;
- Otoscopy/microscopy;
- Tympanometry;
- Pure tone audiometry (air and bone conducted)*;
- Speech audiometry $(WRS_{(80 \text{ dB})} \text{ and } WRS_{(60 \text{ dB})})^{**}$;
- Spontaneous nystagmus (Frenzel goggles)**;
- Balance test (Romberg's test)**;
- Suicidality questionnaire (C-SSRS, Baseline version);
- Blood sampling for laboratory assessment (hematology, biochemistry, virology);
- Urine pregnancy test, if applicable;
- Adverse event reporting.

Prior to randomization, results of all baseline assessments (except hematology, biochemistry and virology results, which will become available only later) will be reviewed. Subjects who do not meet all inclusion criteria and / or who meet one or more of the exclusion criteria are excluded at this point and will not be randomized (screening failures).

Eligible subjects are randomly allocated to either the active treatment (AM-111 0.4 or 0.8 mg/mL) or placebo.

After receiving the single dose of IMP, all subjects will be advised to avoid noisy situations until FUV4, and to protect the ear canal and middle ear of the treated ear from water exposure until the tympanic membrane is closed again.

^{*} Pure tone audiograms measured in subjects presenting within the first 24 hours from ISSNHL onset have to be confirmed by a second measure that is conducted, at the earliest, 24 hours after the onset of ISSNHL. This new confirmatory assessment will serve as baseline value.

^{**} Speech audiometry, spontaneous nystagmus and balance test will be assessed, at the earliest, 24 hours after ISSNHL onset, and this measurement will serve as baseline value.

For the background therapy the investigator prescribes or provides prednisone, prednisolone or methylprednisolone, and the background therapy documentation card documenting the compliance will be handed out to the subject.

7.2 Follow-Up Visits

Subjects enrolled and randomized will be asked to come back for FUV1 on D3 (\pm 1 day), FUV2 on D7 (\pm 2 days), FUV3 on D28 (\pm 5 days) and FUV4 on D91 (\pm 7 days) post-treatment. Unless otherwise specified, the following assessments will be performed at each Follow-up visit:

- Concomitant medications;
- Background Therapy Compliance Card (check and verify at FUV1 and FUV2, return to site at FUV3)
- Tinnitus characteristics;
- Vital signs (blood pressure, temperature, pulse);
- HHIA questionnaire (only at FUV3 and FUV4);
- PGIC (only at FUV2, FUV3 and FUV4);
- Tinnitus presence or absence and numerical rating scales;
- Otoscopy/microscopy;
- Tympanometry (only if the eardrum is fully closed);
- Pure tone audiometry (air and bone conducted);
- Speech audiometry (WRS_(80 dB) at each FUV, WRS_(60 dB) at FUV 4 only);
- Spontaneous nystagmus (Frenzel goggles);
- Balance test (Romberg's test);
- Suicidality (C-SSRS, Since-Last-Visit version);
- Laboratory test (hematology, biochemistry) (only at FUV1);
- Urine pregnancy test, if applicable (only at FUV4);
- Adverse event reporting.

Throughout the follow-up period, subjects will record weekly in a diary the presence or absence of tinnitus and their ratings of tinnitus loudness ($TLQ_{Loudest}$) and tinnitus annoyance (TAQ_{Worst}). Subjects should not have access to their previous ratings. Diary completion compliance should be monitored by the site throughout the trial and should be discussed with the subject (if applicable) at least at each study visit.

7.2.1 Conditional Follow-up Visit

In the event that the tympanic membrane of the treated ear is still open at FUV2 (as defined in Section 9.4.1.3), a conditional follow-up visit (cFUV) should be scheduled on D14 (± 3 days) in order to examine and document the healing process of the tympanic membrane. During this visit the ear canal and tympanic membrane will be examined by otoscopy/microscopy. If the tympanic membrane is closed at this visit, tympanometry will be performed. Additional measures may be conducted as deemed medically indicated by the Investigator. Findings will be recorded in the source documents and the CRF and an AE will be reported as specified in Section 9.4.1.

Additionally, other AEs and changes in concomitant medication will be recorded.

7.3 Subject contact

Subjects will be contacted via phone, text message or email by the Investigator or designee on D56 (± 7 days) to collect information about any AEs and concomitant medication since FUV3. The subject contact and obtained information will be recorded in the subject's source documents and the CRF.

7.4 End of the trial (regular or premature)

If the subject completes all visits as per the protocol, then FUV4 is the regular end-of-the-trial visit.

In case the subject terminates the trial prematurely, for whatever reason, an unscheduled end-of-the-trial visit should be performed at the earliest convenience. This visit follows the same procedures as visit FUV4 (refer to Section 7.2). In case termination occurs before FUV1, blood samples for laboratory assessments as foreseen for FUV1 are to be taken.

8 Study medication and concomitant medication

8.1 Investigational Medicinal Product formulation and packaging

8.1.1 Drug substance

D-JNKI-1 is a stable, water soluble peptide containing 31 amino acids (a 19 amino acid effector domain, a 10 amino acid transporter domain and 2 proline spacers). All amino acids besides the achiral glycine are in D-form.

The chemical name for D-JNKI-1 is: H-D-Asp-D-Gln-D-Ser-D-Arg-D-Pro-D-Val-D-Gln-D-Pro-D-Pro-D-Leu-D-Asn-D-Leu-D-Thr-DThr-D-Pro-D-Arg-D-Lys-D-Pro-D-Arg-D-Pro-D-Arg-D-Arg-D-Arg-D-Arg-D-Arg-D-Lys-D-Arg-Gly-NH2 (IUPAC nomenclature).

8.1.2 Drug product

The IMP is manufactured under aseptic conditions in concentrations of 0.0 (placebo), 0.4 and 0.8 mg/mL D-JNKI-1. provided in prefilled glass syringes filled The placebo formulation is identical to AM-111 except for the active substance, which is lacking.

All the second s		

8.1.3 Manufacturer

The IMP is manufactured in accordance with current Good Manufacturing Practices (cGMP) by:

8.1.4 Labelling and packaging

The IMP is supplied to the trial sites in kits. Each kit contains 1 pre-filled syringe for the treatment of the subject's affected ear.

The IMP is labeled in appropriate local language according to Annex 13 GMP and country specific requirements, packaged, stored, released and distributed according to cGMP by:

Sample labels will be filed in the TMF.

A complete record of batch numbers and expiry dates of all IMP will be maintained in the TMF.

For all IMP, a system of kit numbering in accordance with the requirements of GMP will be used. This will ensure that for each subject, any dose of IMP can be identified and traced back to the original batch ware of the active ingredient.

Lists linking all numbering levels will be maintained by the provider in charge of IMP packaging. Before unblinding, these lists will not be accessible to any individual involved in trial operations.

8.2 Treatment

8.2.1 Dosage form

8.2.2 Route of administration

The IMP is administered intratympanically by the Investigator (see Section 6.8).

8.2.3 Dosing regimen

Subjects wil	ll receive o	ne single	dose	rompalantes de la compa	of IN	√P into	the aft	fected ear	at TV.	Subjects
will receive	either AM	-111 (0.4	and 0.8	mg/mL,	respectivel	y) or p	lacebo.			
AM-111 0.4	· mg/mL 🌃	aret.		ar and the		of AM	[-111 0.	8 mg/mL		

8.2.4 Background therapy

The background therapy (corticosteroid) is self-administered by eligible and consenting subjects for 14 days followed by a 5-day taper, starting on TV (or at the earliest within 36 hours prior to randomization). The background therapy consists of an oral corticosteroid course with prednisolone or methylprednisolone as follows:

- Prednisone or prednisolone 1 mg/kg/day, at a maximum 60 mg/day (taper 50 mg, 40 mg, 30 mg, 20 mg, and to 10 mg), or
- Methylprednisolone 0.8 mg/kg/day, at a maximum 48 mg/day (taper 40 mg, 32 mg, 24 mg, 16 mg, and to 8 mg).

The dose is to be adapted to the next strength available and to be taken undivided in the morning and can be started within 36 hours prior to randomization. If the course is started within 36 hours prior to randomization, the maximum dose will be given from Day -2 until Day 12. If the course is started on TV, the maximum dose will be given until Day 13.

The background corticosteroid treatment may be omitted in case of medical contraindication of oral corticosteroids or if declined by the subject. The investigator will provide a background therapy documentation card for the subject to document the intake of the corticosteroid.

Procurement of the background therapy will be performed by the hospital / site directly.

8.3 Blinding

The Investigators as well as the subjects will be blinded regarding the dose of IMP administered during the trial. This applies also to trial personnel at the Sponsor and the CRO, except for designated unblinded staff at the CRO. In particular, the gel formulation will be of the same appearance for AM-111 0.4 mg/mL, AM-111 0.8 mg/mL and placebo and will reveal no differences during or following injection, neither to the Investigator, nor to the subject. None of the Investigators will be aware of the randomization schedule.

The interim analysis will be performed by an independent statistician. The Sponsor and any persons who are involved in the ongoing conduct and management of the trial shall not see or have access to any group or individual patient unblinded data viewed by the independent statistician, for the duration of the trial.

For reasons and procedures concerning breaking the blind please refer to Section 9.5.

8.4 Storage and drug accountability

The Investigator or designee must confirm the receipt of the study medication (IMP) within the IWRS. The study medication must be stored in securely locked areas that are only accessible to authorized study team members until administered to the subjects.

All subjects will receive their single dose IMP administered at the clinical site. The Investigator or his/her designee must maintain an individual record for each subject. Each drug unit dispensed, received or returned must be recorded.

Study medication must not be used outside the frame of this protocol. The receipt, use, and any loss of study medication will be adequately recorded. An accountability form for all study medication supplies and their disposition subject by subject will be completed and collected by the Investigator or pharmacist and verified by the CRA.

Throughout the trial and at the end before trial site closure, all used IMP pre-filled syringes will be counted by the CRA. Details on return and destruction of IMP will be given in the Operations Manual.

The IMP kits containing the prefilled syringes are to be stored at 36-46°F (2 - 8°C).

8.5 Treatment compliance

The IMP is administered only once and at the site.

However, if the subject requests to refrain from treatment after randomization, but before the IMP administration, the Investigator or designee should encourage the subject to still complete all follow-up visits described in the protocol. Please refer to Section 5.3.

Compliance with the background therapy regimen will be checked via the background therapy documentation card. It will be recorded by the Investigator or designee in the CRF and subject records.

8.6 Prior and concomitant medications

Prior medication means all medication taken before a subject is screened, while concomitant medication refers to all medication taken by the subject during the trial (encompassing TV until end of follow-up). Any medication known to be ototoxic taken up to 3 months before randomization (TV), any medication ongoing or initiated from within two weeks prior to TV and any medication taken during the trial up to FUV4 will be recorded in the source documents and on the CRF. This includes prescription-, non-prescription and herbal medicines as well as vitamins and mineral supplements. This documentation must include the name and dose of each medication, start and end date of use, frequency, route, and the reason for administration. Each concomitant medication entered in the CRF should correspond to either an entry in the subject's medical history, or an AE.

The following treatments are not allowed during the course of the trial (from TV to FUV4):

- Any concomitant pharmacological or non-pharmacological treatment of ISSNHL-related hearing loss or tinnitus (other than the background therapy that may be started up to 36 hours prior to randomization);
- Any therapy known as potentially ototoxic (e.g. aminoglycosides [systemic or ototopical with middle ear exposure], cisplatin, loop diuretics, quinine etc.);
- Any other pharmacological or non-pharmacological treatment for hearing loss other than the IMP and background therapy unless that treatment was taken for another condition prior to the current ISSNHL incident and started at least 4 weeks prior to randomization; such treatment should be continued unchanged throughout the trial.

Subjects will be instructed not to take any prescribed or over-the-counter medications without prior consultation with the Investigator or designee.

8.7 Further treatment after the end of the trial

After the end of the trial, the subjects may be treated according to local standard practice.

9 Adverse events

9.1 Definitions

9.1.1 Adverse Event

An Adverse Event (AE) is any untoward medical occurrence in a subject or clinical investigation subject administered a pharmaceutical product and which does not necessarily have to have a causal relationship with this treatment.

An AE can therefore be any unfavorable and unintended sign (including an abnormal laboratory finding, for example), symptom, or disease temporally associated with the use of the IMP or intratympanic IMP administration procedure, or other trial procedure or other reasons not related to the trial.

An event that emerges during treatment having been absent prior to treatment or worsening relative to the pre-treatment state is defined as treatment emergent adverse event (TEAE).

9.1.2 Serious Adverse Event

An SAE is defined as any untoward medical occurrence that:

- Results in death
- Is life-threatening
- Requires hospitalization or prolongation of existing hospitalization
- Results in persistent or significant disability or incapacity
- Is a congenital anomaly or birth defect
- Is an important medical event that requires intervention to prevent one of the above

These characteristics / consequences have to be considered at the time of the event. For example, regarding a life-threatening event, this refers to an event in which the subject was at risk of death at the time of the event; it does not refer to an event which hypothetically might have caused death if it were more severe. Medical and scientific judgment should be exercised in deciding whether expedited reporting is appropriate in other situations, such as important medical events that may not be immediately life-threatening or result in death or hospitalization, but which may jeopardize the subject or may require intervention to prevent one of the other outcomes listed in the definition above.

Exceptions(s):

- 1) The hospitalization or prolongation of hospitalization as a part of a routine procedure followed by the center (e.g. stent removal after surgery). The procedure must have been scheduled prior to the enrolment into the study.
- 2) The hospitalization for a survey visit, annual physicals, or social reasons.
- 3) Hospitalization qualifies for an SAE only for an inpatient treatment which includes an overnight stay.
- 4) A visit to the emergency room of a hospital without being admitted to inpatient stay regardless of the time of visit does not qualify for hospitalization.
- 5) Elective hospitalizations for pre-existing condition documented in the medical history that had not worsened (e.g. elective hospitalization for a total knee replacement due to a pre-existing condition of osteoarthritis of the knee that had not worsened during the course of the trial).
- 6) Hospitalization for facilitating in-patient treatment of ISSNHL with other treatment options such as, for example, rheologic infusion therapy or hyperbaric oxygen, although these treatments are not permitted as per the protocol and will be documented as major protocol deviations.

9.1.3 Adverse Reaction

All noxious and unintended responses to the IMP related at any dose should be considered adverse reactions. The definition implies a reasonable possibility of a causal relationship between the event and the IMP. This means that there are facts (evidence) or arguments to suggest a causal relationship.

9.2 Assessment of seriousness, causality, expectedness and severity

Seriousness: The judgment as to whether the event is serious or not is made by the Investigator. If the Medical Monitor or Sponsor is of the opinion that an AE should be rated as serious, the SAE form has to be completed by the site.

Causality (causal relationship): An event can be either causally related or not causally related to the IMP, or causally related or not causally related to the intratympanic IMP administration procedure. The Investigator will assess the causal relationship of the AE with respect to:

- the IMP, and / or
- the intratympanic IMP administration procedure.

Related means that there are facts (evidence) or arguments that suggest a causal relationship. Investigators will assign causality at their respective sites during the trial. In case no causality is assigned by the Investigator, the Investigator is encouraged to express an opinion. The Medical Monitor of the trial will review all AE data for the assigned causality. If the Medical Monitor disagrees with the Investigator's causality assessment, the opinion of both the Investigator and the Medical Monitor will be provided.

Expectedness: The expectedness of an adverse reaction is determined by the Medical Monitor and is assessed in the light of the Reference Safety Information (RSI). The RSI is contained in the most current version of the IB. The term "expected", in pharmacovigilance, strictly refers to the event being mentioned or listed in the applicable RSI. It is not used to describe an event which might be anticipated from knowledge of the pharmacological properties of a substance. An event is also not to be described as "expected," merely because it was foreseeable due to the health status (e.g., age, medical history) of the trial subject.

Severity: The following three-point rating scale will be used by the Investigator to rate the maximum intensity of each AE:

- Mild: The subject is aware of signs or symptoms causing minimum discomfort but no disruption of usual daily activities consistent with what would be expected in an uneventful recovery period.
- Moderate: The event is sufficiently discomforting to the subject that it interferes with usual daily activities consistent with what would be expected in an uneventful recovery period (disturbing).
- Severe: Due to the event, the subject is unable to perform usual daily activities consistent with what would be expected in an uneventful recovery period (prevents).

9.3 Pregnancy exposure (exposure in utero)

Becoming aware of a pregnancy during the clinical trial does not necessarily lead to withdrawal of the subject. Pregnant subjects will be instructed to perform all follow-up visits. If a pregnancy is discovered while the subject is receiving background therapy, this therapy must be stopped immediately.

9.4 Reporting

9.4.1 Trial specific rules for reporting

All AEs, including SAEs and clinically relevant abnormalities in laboratory test variables, will be monitored and documented from the time point of ICF sign off during TV until FUV4 (see Section 9.1).

The Investigator should ask the trial subject in a non-leading manner about the state of his/her health in order to elicit information on AEs which may have occurred since the last visit. Any clinically significant observations made during the visit itself also constitute AEs. The Investigator should make an assessment for AEs at each visit and record the events in the source documentation and in the CRF on the "Adverse Events" pages. Follow up information must be entered as soon as available.

Wherever possible, a specific disease or syndrome rather than individual associated signs and symptoms should be identified by the Investigator and recorded on the CRF. However, if an observed or reported sign, symptom or clinically significant laboratory abnormality is not considered a component of a specific disease or syndrome by the Investigator, it should be recorded as a separate AE in the source documents and on the CRF. Additionally, the condition that led to a medical or surgical procedure (e.g., surgery, endoscopy, tooth extraction, transfusion) should be recorded as an AE, not the procedure.

Any medical condition already present at the baseline medical assessment will be documented as medical history. If a medical condition or signs or symptoms present at baseline worsens (e.g. change in severity or seriousness) at any time during the trial, this should be reported as an AE.

SAEs will be followed until the event resolves or stabilizes or up to 2 months after FUV4. The Investigator is obliged to assist with the follow-up of SAEs. In case a SAE occurs after the subject has completed the trial and the Investigator considers this event related to the IMP or trial procedures, it should be reported immediately. The Investigator must contact the CRO Safety Manager to determine how the SAE should be documented and reported.

Any AE that is still ongoing after a subject's final visit will be recorded as ongoing in the CRF. However the Investigator will continue to follow up ongoing SAEs for the time frame described above and record information in the source documents and on the *Follow-Up SAE Form*.

For all AEs the Investigator is responsible for documenting the action taken and the outcome, as specified in the source documents and in the CRF.

The onset date of an SAE is the time as of which the event fulfils a criterion for seriousness, which will be captured on the SAE page in the CRF. For details on documenting worsening of hearing and worsening of tinnitus refer to Sections 9.4.1.1 and 9.4.1.2.

Adverse events which occur during the trial should be treated by established standards of care that will protect the life and health of the subject.

9.4.1.1 Worsening of hearing

A worsening of hearing in the treated ear is not to be recorded as AE. Any change of hearing thresholds and word recognition scores is subject of analysis under this protocol. The subject's subjective sensations will be captured by patient reported outcome measures (HHIA, PGIC).

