2.3.2 Summary of accumulated adverse event data

A total of 221 subjects were included in the two clinical trials conducted with AM-111 (AM-111-AAT-PI, AM-111-CL-08-01). Seventy-five subjects received a single dose AM-111 at a concentration of 0.4 mg/mL (low dose), 74 subjects received AM-111 at the concentration of 2.0 mg/mL (high dose) and 72 subjects were randomized to receive the matching placebo.

In subjects who received any dose of AM-111, 57 patients reported at least 1 adverse event, of which 18 reported treatment-related AEs. Only four treatment-related adverse event terms were reported in more than 1 patient, and these were tinnitus (7 patients, 4.7%), hearing impaired (6 patients, 4.0%), ear pain (3 patients, 2.0%), and incision site complications (2 patients, 1.3%). Ear discomfort, vertigo, autophony, otitis externa, otitis media, nausea and otoacoustic emission test abnormal were each reported by 1 patient. One serious adverse event (SAE) of deafness neurosensory was considered related to study drug. No fatal or life-threatening AE was reported.

The majority of AEs were local, mild or moderate in severity and concerned hearing and tinnitus. Detailed analysis of hearing deterioration at Days 3 and 7 pointed most often to the ongoing underlying pathology as cause; three cases were related to the myringotomy, and one case to middle ear infection (fully resolved). The majority of tinnitus-related AEs was observed only after Day 7 and thus considered unrelated. The number of subjects with procedure-related AEs (ear discomfort or pain, incision site complications, middle ear infection) was < 5%. By Day 7, the tympanic membrane was closed again in all patients except 7 (mild, fully resolved subsequently). Vital signs essentially remained stable throughout the observation period, and the incidence of spontaneous nystagmus decreased in all treatment groups. Further details of the adverse event profile are provided in the Investigator Brochure of AM-111.

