5.4.2 Premature trial termination

Subject enrolment and randomization will be stopped if, based on a review of safety and tolerability data by the Sponsor, further study treatments are deemed not acceptable.

The Sponsor reserves the right to discontinue the trial at any time and for any reason. In the event of emerging evidence from literature or other scientific sources demonstrating that the investigational drug may be ineffective or may affect the subjects' safety, the Sponsor will decide about trial termination.

In addition, the Sponsor reserves the right to discontinue a trial site in case of major protocol deviation or insufficient enrolment.

6 Trial procedures

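### The rule that treated-ear hearing worsening is never an AE makes no exception for serious or related events and clashes with the protocol's own SAE rules

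*Protocol*

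**What the plan says.** Protocol 9.4.1.1 states: "A worsening of hearing in the treated ear is not to be recorded as AE". It gives a reason: "Any change of hearing thresholds and word recognition scores is subject of analysis under this protocol". Symptoms are left to two questionnaires, the HHIA and the PGIC. Nothing in the section refers to seriousness, relatedness, size or permanence.

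The parent section, 9.4.1, has a general rule that begins "If a medical condition or signs or symptoms present at baseline worsens (e.g. change in severity or seriousness) at any time during the trial" and ends by requiring an AE report. Directly after its rule on the onset date of an SAE, the same section adds: "For details on documenting worsening of hearing and worsening of tinnitus refer to Sections 9.4.1.1 and 9.4.1.2".

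Section 9.1.2 defines an SAE by its consequences, one of which is lasting or significant disability. It lists six exceptions. The only one tied to the study disease concerns hospital admission for other ISSNHL treatments; hearing worsening itself is not listed. Section 9.4.2 requires every SAE to be reported within 24 hours, whatever its causality.

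On past experience, Protocol 2.3.2 reports: "One serious adverse event (SAE) of deafness neurosensory was considered related to study drug".

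**The concern.** Hearing loss in the injected ear is the harm that the protocol itself chose as its primary safety endpoint, and it is the type of the one earlier SAE that 2.3.2 reports as related to study drug. A site that sees a severe further loss after the injection must decide whether to report it. One section tells it not to record an AE. Two others, read alone, tell it to report an SAE.

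If the site follows 9.4.1.1, the event gets no causality rating, no check against the reference safety information and no prompt report. It also leaves no trace in the SAP's tables of related and serious TEAEs, so a reader of those tables could take an empty row to mean that no such harm occurred.

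**Working it through.** **1. Which rule governs.** Two readings are possible.

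- *Reading A: 9.4.1.1 governs.* Section 9.4.1 opens by counting SAEs among AEs, and the pointer to 9.4.1.1 stands directly after the SAE onset rule. On this reading, something that is not an AE cannot be an SAE.
- *Reading B: 9.1.2 and 9.4.2 govern.* The SAE definition is not limited to recorded AEs, hearing worsening is not among its six exceptions, and 9.4.1.1 does not mention SAEs.

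The protocol does not choose between them.

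**2. What happens to a case.**

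| Worsening in the treated ear | Reading A | Reading B |
|---|---|---|
| Serious (9.1.2) | Not recorded, no 24-hour report | SAE, reported within 24 hours |
| Related, not serious | Not recorded | Not recorded; 9.1.2 does not apply |
| Neither | Not recorded | Not recorded |

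The contradiction therefore concerns serious events. For related but non-serious events there is no competing SAE rule, only an exemption without a limit.

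**3. What the separate capture provides.** The primary safety endpoint (Protocol 10.2.1) counts threshold rises of at least 10 dB averaged over two adjacent frequencies, from baseline to FUV3; Protocol 10.2.2 adds the other follow-up visits. SAP Tables 14.3.4.3.2, 14.3.4.3.4 and 14.3.4.3.5 report these counts. They carry no case-level seriousness, causality or expectedness. Causality is assessed for AEs (Protocol 9.2), and the SAP's AE tables are built from TEAEs (SAP 10.1.2.1). Audiometry is scheduled at D3, D7, D28 and D91. The D56 contact collects only AEs and concomitant medication (Protocol 7.3), so a hearing collapse reported then has no designated place.

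**4. Size, from the earlier programme (Protocol 2.3.2).** The document's figures reproduce first:

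- AM-111 subjects: 75 + 74 = 149; with placebo, 149 + 72 = 221.
- Related hearing impaired: 6/149 = 4.03% (stated 4.0%).
- Related tinnitus: 7/149 = 4.70% (stated 4.7%).
- Ear pain: 3/149 = 2.01% (stated 2.0%).
- Incision site complications: 2/149 = 1.34% (stated 1.3%).
- Hearing impaired as a share of AM-111 subjects with a related AE: 6/18 = 33%.

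The exact (Clopper-Pearson) 95% interval for 6/149 runs from the 2.5% point of Beta(6, 144) to the 97.5% point of Beta(7, 143): 1.5% to 8.6%.

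As an illustration, assume that the earlier rate and recording practice carry over. Expected related cases = n × p:

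- Planned active subjects, 100 + 100 = 200: 200 × 6/149 = 8.1 (range 3.0 to 17.1).
- Active subjects at termination, assuming that 1:1:1 held, 56 × 2/3 ≈ 37: 37 × 6/149 = 1.5 (range 0.6 to 3.2).

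For an event like the single deafness SAE, P(at least one) = 1 − (1 − p)^n. Its arm is not stated, so two rates are shown:

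- p = 1/149: 74% with n = 200; 22% with n = 37.
- p = 1/221: 60% with n = 200; 15% with n = 37.

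Under 9.4.1.1 as written, the AE tables would show none of the non-serious related cases. Under Reading A they would show none of the serious ones either.

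**The case against.** The strongest reply is that the exemption is deliberate and sensible. The outcome under study is hearing, the natural course is variable, and an objective measurement by arm is better evidence than scattered AE reports. The 10 dB threshold is stricter than the 15 dB used in the earlier trials (Protocol 2.5.2), both conduction routes are examined, and the untreated ear serves as a comparator. Protocol 2.3.2 attributes most earlier deterioration to the underlying disease, with three cases ascribed to the myringotomy and one to infection. Section 2.5.2 reports no apparent difference in local AEs between arms. All of this stands. It justifies the exemption for ordinary worsening, but it does not supply a case-level assessment for a serious or related event.

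Four stronger readings are tempting and should not be drawn.

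- *A serious hearing loss has no expedited route.* Sections 9.1.2 and 9.4.2 provide one if read alone. The route is contradictory, not absent.
- *Section 9.4.1.1 contradicts the general rule on worsened baseline conditions.* That is a general rule with a signposted exception. The real clash is with the SAE text.
- *The stopping provision cannot see hearing harm.* Section 5.4.2 is "based on a review of safety and tolerability data by the Sponsor", which is not limited to AE data, and pure tone audiometry is a listed safety assessment.
- *A fixed share of related AE reports is lost.* The protocol gives no total of related reports. Summing the listed terms would leave out the deafness SAE and would mix in tinnitus, which has its own rule (9.4.1.2) and remains an AE when new.

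**Conclusion.** The point holds as a gap and an internal contradiction in safety reporting. Section 9.4.1.1 exempts all treated-ear hearing worsening without regard to seriousness or relatedness, and the protocol does not say whether it or the SAE text prevails. The loss is in case-level assessment, prompt reporting and the related and serious TEAE tables. Hearing harm as such is not missing from the safety analysis.

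The documented scale is 6 of 149 AM-111 subjects (4.0%) with treatment-related hearing impairment, plus one related deafness SAE of unstated arm. The projections of about 8 cases in 200 active subjects, or 1 to 2 in about 37, are illustrations. The earlier trials also enrolled acute acoustic trauma, used 0.4 and 2.0 mg/mL, and did not separate drug from procedure effects. No corresponding placebo rate is given, so these counts are not an excess over placebo. No sample size, power or efficacy conclusion depends on this point.

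**What to change.** Reconcile 9.4.1.1 with 9.1.2 and 9.4.2. Keep the exemption for worsening that is neither serious nor related. Add one sentence to 9.4.1.1: treated-ear worsening that meets a criterion in 9.1.2, or that the investigator judges related to the IMP or the injection procedure, is recorded as an AE or SAE and, if serious, is reported under 9.4.2.

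In the SAP, footnote the exemption on the TEAE tables (14.3.1.1 to 14.3.1.12) and refer the reader to Tables 14.3.4.3.2, 14.3.4.3.4 and 14.3.4.3.5. The hearing counts need not be moved beside the TEAE overview; that is layout.

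The cost is one protocol sentence and one footnote. Some events will appear both as an AE and in the endpoint, which the footnote can explain. Relatedness will sometimes be hard to separate from the natural course. Recruitment stopped on 28 November 2017 at 56 subjects (SAP 4), so the protocol sentence can affect only remaining follow-up or later protocols; the footnote still helps readers of this trial's report. Label: cheap improvement.
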